Enrollment date is the date the patient signs the Informed Consent Form to participate in this study.

Enrollment date cannot occur earlier than index/baseline date.

Target Population

The main patient population for this study are new users of faricimab approved in nAMD and DME in at least one eye.

Patients must meet the following criteria for study entry:

1. Adult patients (≥ 18 years), who have provided signed informed consent, as required per local regulations.
2. Patients as defined by local regulations and local faricimab product label, who are initiating treatment with faricimab at time of enrollment or have initiated treatment with faricimab within 3 months prior to patient enrollment, in DME or

nAMD in at least one eye according to the investigator's discretion in routine clinical practice for anti-VEGF treatment naïve and pre-treated patients.

3. Patients have received at least one faricimab treatment (the first dose) in the study eye.

Patients who meet any of the following criteria will be excluded from study entry:

1. Concomitant participation of the patient in any investigational ophthalmology clinical trial that includes receipt of any ophthalmological investigational drug or procedure within the last 28 days prior to enrollment.
2. Current participation in any interventional clinical study
3. Active ocular inflammation or suspected/active ocular infection in either eye.
4. Patients in whom the study eye has been treated with faricimab for more than 3 months prior to enrollment.
5. Patients treated with faricimab who have and are currently participating in patient support programs that are Market Research and Patient Support Programs (MAPs) including Post Trial Access Programs (PTAP) and Compassionate Use Programs (CUP), will be excluded from selection.
6. Patients with non-ocular sight threatening disease which have an effect on primary endpoint (VA) eg: apoplexia.
7. Hypersensitivity to the active substance or any of the excipients of Vabysmo (as per label)

Studied Medicinal Products

The studied medicinal product within this study is faricimab.

The dosing and treatment duration of faricimab are at the discretion of the physician and agreement of the patient, in accordance with local clinical practice and local labeling.

Variables

Only variables obtained according to routine clinical practice can and should be documented in this study.

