The variables collected at index date, enrollment (incl. retrospective data) and during follow-up fall into the following categories:

Primary and Secondary Effectiveness Variables

- Visual Acuity (VA) on approximate ETDRS letter score (see [Appendix 3](#)) (by eye) in nAMD and DME (including date, method of VA assessment - scale and type of correction), as measured per local clinical practice.
- Treatment regimens (i.e., Fixed regimen, treat-and-extend (T&E), PRN, Other - see [Appendix 5](#)).
- Faricimab intravitreal injections/dates of treatments
- Visits with or without treatment (observational), dates of visits.
- Eyes with treatment switch, including date and reason for switch.
- Eyes obtaining treatment intervals of Q8W, Q12W, Q16W and other
- Loading dose of intravitreal injections
- Central Subfield Thickness (CST) and anatomical observations (including method, software settings and type of optical coherence tomography [OCT]) (as measured per local standard clinical practice).

Exploratory Effectiveness Variables

- Imaging assessments (by eye), as per routine clinical practice (during visits for the retinal indications) e.g.:
 - IRF
 - SRF
 - serous PED and height if measured.
- Specific Exploratory Variables for nAMD
 - Eyes with presence/absence of atrophy*
 - Eyes with presence/absence of fibrosis**
 - Eyes with presence/absence of serous PED*** (also height of PED if measured)
 - Eyes with presence/absence of hemorrhage****
- Specific Exploratory Variables for DME
 - Eyes with presence/absence of ERM in the central 3 mm (as evaluated by the treating physician)

Health Economic Evaluation Variables (for All Eyes - Both Naïve and Pre-treated)

- For eyes pre-treated with any intravitreal anti-VEGF:
 - Type of intravitreal anti-VEGF treatments received before index date
 - Number and dates of previous anti-VEGF treatments

- Treatment interval of the last preceding anti-VEGF treatment before entering the study.
- For all eyes (both naïve and pre-treated) the below will be collected following the index date:
 - Treatment regimen (i.e., Fixed regimen, T&E, PRN, Other).
 - Number of intravitreal faricimab injections (with date).
 - Number of visits with or without treatment (observational) with dates.

Safety Variables

- Safety events (all ocular and non-ocular adverse events [AEs]) including, date, seriousness, severity and outcome.

Other Variables of Interest

- Patients' characteristics of interest include but are not limited to:

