 - Demographic characteristics
 - Relevant medical history: ocular and non-ocular (ocular - by eye where applicable):
 - Comorbidities (ocular and non-ocular)
 - Prior intravitreal anti-VEGF treatments (type, dates) – by eye - until entry into the current study
 - Previous intravitreal treatments (IVT) other than anti-VEGF and other ocular treatments
 - Surgical history: macular laser, surgical procedures, corneal transplant, cataract surgery, vitrectomy, peripheral laser treatment, yttrium aluminum garnet (YAG) laser treatment, corneal surgery, steroid implant.
 - Concomitant medications (ocular and non-ocular)
 - Specific baseline***** characteristics:
 - For nAMD patients:
 - Type of membrane (1-3 macular neovascular membrane (MNV), polypoidal choroidal vasculopathy (PCV), cystoid macular edema (CME))
 - Pigment epithelial detachment (PED) or disruption within the retinal pigment epithelium
 - Duration of the disease
 - Presence/absence of atrophy*
 - Presence/absence of fibrosis**
 - For DME patients:
 - Severity of diabetes (HbA1c levels),

- Duration of diabetes
- Diabetes type
- Duration of DME
- DME classification (central involvement /non-central involvement). Central is defined as central 3 mm.
- Presence/absence of proliferative diabetic retinopathy
- Presence/absence of ERM in the central 3 mm

*Atrophy definition: Defined as cRORA (complete loss of photoreceptors and retinal pigment epithelium (RPE) in the central 3 mm), atrophy is to be assessed as per the treating physician (Sadda S et al 2018, Guymer RH et al 2020, Savastano MC et al 2020).

**Fibrosis: Hyperreflective material below the neurosensory retina on OCT (may have a multilaminar appearance) accompanied by different amounts of RPE destruction & photoreceptor loss. It is to be evaluated by the treating physician in the central 3 mm. (Willoughby AS et al 2015, Gräfe MGO et al 2020).

***Serous PED: Separation between the RPE and the inner most aspect of Bruch's membrane. Is to be evaluated in the central 3 mm.

****Hemorrhage to be evaluated by the treating physician in the central 3 mm

*****Baseline characteristics will be documented at the timepoint of faricimab treatment initiation (index date) for the respective eye included in the study

- Treatment and management (by eye) during the study period, from index date until the end of study participation, include but not limited to:
 - Treatments received for the indications (nAMD, DME)
 - Treatment discontinuation/termination

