 - Details of other procedures that could potentially elevate/deteriorate VA.
- Imaging assessments (by eye) during the study period from index date until end of study participation, include but not limited to:
 - optical coherence tomography (OCT)-imaging assessment type, machine used, and the results of CST, IRF, SRF, PED. Images will not be collected.

The primary effectiveness variable is VA. VA will be collected as measured per local practice and will then be entered from source data into electronic case report form (eCRF) using the approximate Early Treatment Diabetic Retinopathy Study (ETDRS) letter score.

Data Sources

Patients' data will be recorded on eCRFs and stored in the electronic data capture (EDC) system. All clinical data will be processed and stored in a database. All data will be pseudo-anonymized, and each patient will have a unique code so that the information of the same patients can be linked.

Faricimab—F. Hoffmann-La Roche Ltd
Protocol MR45586, Version 1.0

Data Analysis

Full details of the statistical analysis to be conducted will be provided in the SAP.

The following 2 cohorts will be defined and analyzed:

- Cohort 1: Patients receiving faricimab for nAMD in at least one eye
- Cohort 2: Patients receiving faricimab for DME in at least one eye.

Within each cohort, sub-cohorts will be defined as per treatment history at eye-level when initiating faricimab for this study as described below.

The following sub-cohorts will be considered:

- A. Treatment naïve sub-cohort:
Patient-eyes initiating faricimab intravitreal treatment that have never had any anti-VEGF intravitreal treatment
- B. Previously treated with anti-VEGF sub-cohort
Patient-eyes initiating faricimab intravitreal treatment after being previously treated with any intravitreal anti-VEGF.

Sub-cohort Details per Cohort

Cohort 1	Cohort 2
Patients receiving faricimab for nAMD in at least one eye	Patients receiving faricimab for DME in at least one eye
A. Treatment naïve sub-cohort: Patient-eyes newly initiating faricimab intravitreal treatment* in at least one eye that has never had any anti-VEGF intravitreal treatment	A. Treatment naïve sub-cohort: Patient-eyes newly initiating faricimab intravitreal treatment* in at least one eye that has never had any anti-VEGF intravitreal treatment

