To evaluate the correlation/association between retinal treatment characteristics (durability and treatment patterns) and change in VA over time in nAMD and DME	
 ● Change in VA (approximate ETDRS letter score - see Appendix 3) from index date* to months 3, 6, 12 and 24, in relation to: 
 ○ Treatment regimen (Fixed, T&E, PRN, Other - see Appendix 5) ○ Number of intravitreal treatments ○ Total number of visits ○ Treatment intervals ○ Type of pre-treatment and number of previous injections for preceding regimen at index date ○ Length of diagnosis of disease at index date

CST = central subfield thickness, DME = diabetic macular edema, ETDRS = Early Treatment Diabetic Retinopathy Study, nAMD = neovascular age-related macular degeneration, PRN = pro re nata, T&E = Treat-and-Extend, VA = visual acuity, VEGF = vascular endothelial growth factor

*Index date is defined as the date of first faricimab treatment on eye-level. If both eyes are treated with faricimab and the treatment start dates are different, each start date will be used as index date for the respective eye.

**Loading phase is defined as per local label (for nAMD and DME)

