6.7.4.2 Specific Exploratory Analyses for Health Economic Perspective

Exploratory analyses for health economic perspective will be performed per cohort (nAMD, DME) and per sub-cohort (treatment naïve and pre-treated), at the eye-level, based on effectiveness dataset.

The following will be calculated for anti-VEGF pre-treated eyes (pre-treated sub-cohorts) in nAMD and DME and summarized descriptively:

- Type of anti-VEGF treatments received before index date
- Time spent on each pre-treatment
- Number of previous injections for previous treatment
- Treatment interval of the last preceding treatment before entering the study.

The following will be collected prospectively starting at index date, calculated per cohort (nAMD, DME) and sub-cohort (treatment naïve and pre-treated) and summarized descriptively (at index date, 3, 6, 12, 24 months):

- Number and percentage of eyes in each treatment regimen (i.e., Fixed regimen, T&E, PRN, Other).
- Number of injections per eye per year.

- Total number of visits (per eye per year)
- Number of visits with treatment (per eye per year)
- Number of visits without treatment (observational) per eye per year
- Time intervals between treatments, per eye per year.

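### Two pre-treatment history items are cut off at study entry instead of the eye's index date, so faricimab's own early doses can be recorded as prior treatment

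*Protocol*

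**What the plan says.** Two cut-off dates are used for pre-treatment history.

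**Cut off at study entry**
- The last interval, in the Synopsis (Health Economic Evaluation Variables): "Treatment interval of the last preceding anti-VEGF treatment before entering the study". Table 1 in Section 6.3 has the same item. The exploratory objectives (Synopsis and Section 5.2.3) and the planned analysis in Section 6.7.4.2 have a version without the drug class: "Treatment interval of the last preceding treatment before entering the study".
- The treatment history, in the Synopsis (Other Variables of Interest): "Prior intravitreal anti-VEGF treatments (type, dates) – by eye - until entry into the current study".

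**Cut off at the index date or at faricimab initiation**
- Pre-treatment type, in the same Synopsis list as the interval: "Type of intravitreal anti-VEGF treatments received before index date".
- The VA association analysis in Section 5.2.1: "Type of pre-treatment and number of previous injections for preceding regimen at index date". The subgroup list in Section 6.7.4.4 uses the same anchor.
- Sub-cohort membership, defined in the Synopsis (Data Analysis) "as per treatment history at eye-level when initiating faricimab for this study", and similarly in Section 6.7.

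On the order of the dates, the Synopsis and Section 6.1.1 state: "Enrollment date cannot occur earlier than index/baseline date". Enrollment is the day of consent. Inclusion criterion 2 allows faricimab to start at enrollment or up to 3 months before it, and criterion 3 requires that the first dose has been given.

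**The concern.** The health-economic question sets earlier anti-VEGF treatment against current treatment with faricimab (Section 4.1). That needs a clean boundary between the two, and for an eye the natural boundary is its first faricimab injection. Study entry is a different date and can fall well into the faricimab initiation phase.

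The wording does not keep faricimab out of the history. Section 6.7.3 refers to faricimab alongside any other anti-VEGF treatment, which places it in that class. Sections 5.2.3 and 6.7.4.2 ask only for the last preceding treatment, which covers faricimab however it is classed. In Appendix 2, as the table reads, the prospective period starts the day after enrollment, and the retrospective column is marked only for prior treatment and management. A faricimab injection between index and enrollment could therefore be entered as history, while Table 1 also collects it on study from the index date.

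At stake is a descriptive measure of how often the earlier drug was given. If the true prior interval was longer than about 4 weeks, recording faricimab's initiation interval in its place makes the earlier drug look more burdensome than it was.

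**Working it through.** The protocol gives no figure for this point, so there is nothing to reproduce. The check is how many faricimab doses can fall on or before entry.

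**Inputs**
- Lag L from first faricimab dose to enrollment: 0 to 3 months, taken as 0–91 days (inclusion criterion 2).
- Initiation pattern: four monthly doses as described in Appendix 5, used only as an illustration because actual dosing is left to the physician (Section 6.2.3). Two versions: days 0, 28, 56, 84; or calendar months, days 0, 30.4, 60.9, 91.3.
- Distribution of L: not given. Uniform over the 92 whole days 0–91 is an assumption.

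**Step 1. Doses on or before entry, 4-weekly.** Number = 1 + floor(L/28).

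| Lag (days) | Faricimab doses by entry | Faricimab-to-faricimab interval exists? |
|---|---|---|
| 0–27 | 1 | No |
| 28–55 | 2 | Yes, about 4 weeks |
| 56–83 | 3 | Yes |
| 84–91 | 4 | Yes |

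On calendar-month dosing the count is 1 to 3 by day 91. Counting strictly before entry, same-day enrollment gives 0 doses.

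**Step 2. Share of eyes whose last interval could be faricimab's.** This needs at least two doses by entry.
- 4-weekly: L ≥ 28, so 64/92 = 0.696.
- Calendar-month: L ≥ 31, so 61/92 = 0.663.

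Under the uniform assumption this is about 66–70%. Without it, the share is 0% if every patient enrolls at initiation and 100% if every patient enrolls at least a month later.

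**Step 3. Mean number of faricimab doses in the entry-dated history, same assumption.**
- 4-weekly: 1 + 64/92 + 36/92 + 8/92 = 2.17.
- Calendar-month: 1 + 61/92 + 31/92 = 2.00.

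**Step 4. Effect on a recorded interval, if sites follow the literal wording.** Recorded mean = (1 − p) × I + p × 4 weeks, where I is the true prior interval (assumed) and p is the share from Step 2. With p = 0.696:
- I = 6: 0.304 × 6 + 0.696 × 4 = 4.6 weeks
- I = 8: 0.304 × 8 + 0.696 × 4 = 5.2 weeks
- I = 10: 0.304 × 10 + 0.696 × 4 = 5.8 weeks

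At p = 0 there is no change. At p = 1 every value becomes 4 weeks.

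**Step 5. After the correction.** With the cut-off strictly before the eye's index date, the number of faricimab doses in the history is 0 at every lag, and the last interval can only be that of the earlier agent.

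**The case against.** The best defence is that the protocol's structure already separates the two streams. Section 4.1 contrasts previous anti-VEGF treatment with faricimab, and Section 6.1.1 limits the retrospective anti-VEGF data to pre-treated patients' earlier treatments. Appendix 2 has separate rows for prior and on-study treatment, and the Synopsis collects faricimab injections from the index date under their own bullet. Entering the study is not separately defined, and at eye level the study period is described as starting at the index date. No sentence says that faricimab counts as prior treatment. Dates of prior injections are listed, so the SAP could apply the index date later.

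Much of this stands, and it makes the defect a conflict between intent and wording, not a stated rule to count faricimab. It does not remove the defect. Consent is among the criteria for study entry in Section 6.2, so reading entry as enrollment is natural, and one list uses two different terms without saying that they mean the same date. Later repair is not assured either: Table 1 lists the interval itself as a collected variable and, for dates, only that of the first anti-VEGF treatment. A summary interval entered by the site might not be recomputable.

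A reader might infer more than the text supports:
- *Naïve eyes become pre-treated.* Sub-cohort status is set at faricimab initiation. Under the literal alternative every eye would be pre-treated, which contradicts the planned 40/60 split.
- *Counts of previous injections are inflated by about two.* Counts for the VA association and the subgroups are tied to the index date, and the other count items carry no entry cut-off. The figure in Step 3 applies only to the history line dated to entry.
- *Every pre-treated eye gets a faricimab interval.* Same-day enrollment is allowed, and two or more doses by entry are needed.
- *Interval extension on faricimab is overstated.* Section 6.7.4.2 summarizes prior and on-study intervals separately. No analysis of change in interval is specified.

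**Conclusion.** The point holds in a limited form. Two items, the last preceding treatment interval and the history of prior anti-VEGF types and dates, have the wrong cut-off as written and conflict with the index-date anchor used for related items. Because entry can fall up to 3 months after the first faricimab dose, the literal wording admits faricimab doses into the history (up to four by day 91 under 4-weekly dosing). For eyes with at least two such doses, it allows faricimab's own interval to stand in for the earlier drug's.

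The size cannot be fixed from the protocol. The share of eyes exposed lies between 0% and 100%; the 66–70% figure depends on uniform lags and roughly monthly dosing, and the interval shifts in Step 4 also assume that sites record the item literally. The damage is confined to exploratory, descriptive health-economic and treatment-history outputs. The primary endpoint, the naïve/pre-treated split, the index-anchored injection counts and the sample size are not affected.

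**What to change.** Replace the study-entry cut-off with *before the index date of that eye* wherever either item appears:
- Synopsis: exploratory objectives, Health Economic Evaluation Variables, and Other Variables of Interest
- Section 5.2.3
- Table 1 in Section 6.3
- Section 6.7.4.2

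Add one sentence saying that faricimab injections on or after an eye's index date are not prior treatment for that eye. Add an eCRF check that every prior-treatment date precedes that eye's index date.

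The cost is a wording change and one edit check, with no additional data. It should be done at the collection stage, because an interval entered as a summary value may not be correctable in the analysis.

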3 PROTOCOL AMENDMENTS AND UPDATES

Any protocol amendments will be prepared by the Marketing Authorization Holder or designee.

Protocol amendments will be submitted to the Institutional Review Boards (IRBs)/Ethics Committees (ECs) and to regulatory authorities in accordance with local regulatory requirements.

Approval must be obtained from the IRB/EC and regulatory authorities (as locally required) before implementation of any changes, except for changes that involve logistical or administrative aspects only (e.g., change in Site Operations Representative or contact information).

Substantial protocol amendments/updates so far: none.

4 RATIONALE AND BACKGROUND

Retinal vascular diseases, which are often characterized by leakage of fluid, hemorrhage, and fibrous scarring in the eye, include dry and wet forms of age-related macular degeneration (AMD), diabetic retinopathy (DR) and diabetic macular edema (DME), and retinal vein occlusion (RVO). These diseases are major causes of visual impairment and blindness worldwide (Daien et al., 2019; Duphare et al., 2020; Li et al., 2020).

DME is a complication of DR, which is one of the most common microvascular complications of diabetes. Nearly 100 million people worldwide have some signs of macular edema secondary to diabetes. In a literature review by Diabetes Atlas (Thomas, 2019), for the period between 2015 and 2018, the global prevalence of DR (any type) was 27.0%, comprising 25.2% non-proliferative DR and 1.4% proliferative DR, while the global prevalence of DME was 4.6%. The highest prevalence of DR and DME has been reported in African countries (Ethiopia, Tanzania, South Africa, Zambia) at 33.8%, Middle East and North Africa region at 33.8% (one study in Iran), and the Western Pacific region (Singapore, Australia, Hong Kong, New Zealand, Indonesia, China) at 36.2%. The lowest prevalence has been reported in Europe at 20.6% and South-East Asia at 12.5%. In the Occident, the prevalence of any diabetic eye disease was 40.3% in the United States (US) with the prevalence of sight threatening DR 8.2%; while in Europe, the prevalence was found to be 25.7% for DR and 3.7% for DME (Li et al., 2020). It is predicted that the total numbers of inhabitants from the European Union with diabetic eye disease will likely increase from 6.4 million persons as of 2020 to 8.6 million in 2050 (Li et al., 2020).

The critical pathophysiology of DME involves disruption of the blood–retinal barrier, which separates retinal photoreceptors from the vasculature; however, the process is complicated and involves various inflammatory markers upregulated by advanced glycation end products, hyperglycemia, and diabetes. Vasoconstriction caused by diabetes upregulates the expression of vascular endothelial growth factor (VEGF), and this leads to development of macular edema by causing retinal fluid leakage (Ndisang, 2014; Duphare et al., 2020).

Furthermore, the cytokine angiopoietin-2 (Ang-2) and VEGF-A cause destabilization of retinal blood vessels, formation of new leaky blood vessels, and increase in inflammation (Scholz et al., 2015; Sahni et al., 2019). Thus, in recent years, DME management has involved an increased focus on improving these key physiological targets.

Another retinal complication and a leading cause of vision impairment is AMD. AMD is a neurodegenerative disease of the central retina, which is characterized by choroidal neovascularization (CNV) and causes irreversible destruction of the macula and loss of the sharp, central vision (fine detailed vision) required for important everyday activities such as reading, driving, recognizing faces (Holekamp, 2019). As per a systematic review (until 2013) and meta-analysis, 8.7% of the population worldwide had any AMD, and it is projected to affect nearly 288 million people by the year 2040 (Wong et al., 2014). It is well established that early AMD may progress to dry AMD or wet AMD, the latter one is also referred to as neovascular age-related macular degeneration (nAMD) (Chakravarthy et al., 2020). The pathophysiology of nAMD involves the growth of immature blood vessels toward the outer retina from the underlying choroid, along with fluid leak below or within the retina (Ambati, 2012). The cytokines VEGF-A and Ang-2

have been observed to play a pivotal role in neovascularization and vascular complications of nAMD as described previously. Of note, higher levels of Ang-2 correlate with the higher disease severity of nAMD, thus indicating worse best-corrected visual acuity (BCVA) and greater central macular thickness (Ng et al., 2017). Therefore, VEGF and the associated regulators are currently key therapeutic targets for treatment developments for retinal pathologies involving angiogenesis (i.e., nAMD and DME) (Khan, 2020).

Considering the critical pathogenesis of these retinal complications, the emergence of anti-VEGF agents has been a resounding success and breakthrough in the treatment of retinal vascular disorders. Individuals on this treatment usually benefit from this therapy, at least for the first few years, if treated sufficiently to control the neovascular activity.

However, in the long-term, the real-world visual acuity (VA) results have been reported to decline, which could be attributed to less frequent treatment over time, late complications (atrophy and fibrosis), and having a more diverse patient population than clinical trials (including those with comorbidities) (Holz et al., 2015; Jaffe et al., 2019; Ciulla et al., 2018; Khanani et al., 2020). These factors can all impact the outcomes and may lead to loss of vision. Results from landmark registries have confirmed that the number of intravitreal anti-VEGF injections is an important factor linked with better long-term VA related treatment outcomes after 1 and 2 years of therapy (Gillies et al., 2015; Wecker et al., 2017; Westborg et al., 2017; Holz et al., 2020b). Thus, understanding such treatment drivers and risk factors contributing to the differences in real-world outcomes compared to the outcomes in controlled clinical trials is critical to providing maximum and long-term benefits to each individual from the available therapies, with lower societal costs.

An important treatment outcome for anti-VEGF therapy besides improvement of BCVA (defined as the best possible vision that an eye can achieve with the help of an intervention), is a completely dry retina, as the retinal fluid is a biomarker of disease activity. However, evidence suggests that this may not be necessary or desired. Some reports on nAMD indicate that tolerating a certain level of subretinal fluid (SRF) might be desirable and associated with better VA (i.e., the clarity or sharpness of vision) (Jaffe et al., 2019). In the FLUID study (Guymer et al., 2019), patients treated with ranibizumab treat-and-extend regimen (T&E) for 24 months with tolerance for SRF up to 200 µm, achieved visual outcomes non-inferior to those with no tolerance to SRF. Another study showed that during the nAMD treatment with anti-VEGF, a greater variation in the retinal thickness was associated with worse BCVA, as well as development of fibrosis and macular atrophy, among the analyzed patients (Evans et al., 2020). Thus, exploring associations between functional and morphological parameters through long-term real-world observations would be beneficial.

A recent (2019) systematic literature review indicated that there are numerous existing real-world data (RWD) sources on patients with retinal disease treated with anti-VEGFs; however, very few of these have covered the holistic aspects of management of such patients. None of the studies have analyzed treatment patterns across different regions or the treatment regimen dependent outcomes in this cohort of population. Lastly, the safety outcomes (ocular and non-ocular adverse events [AEs]) were reported in only 30% (n=19) of the analyzed RWD sources (Daïen et al., 2019).

Thus, a valuable addition to this existing literature would be a study that develops a robust database that can provide information on overall aspects of treatment and management of these patients. This would inform and assist the healthcare professionals (HCPs) in making sound clinical decisions for individuals on anti-VEGFs and anti-VEGF/Ang-2 in retinal indications.

Faricimab is a novel, bispecific antibody used to treat retinal diseases like nAMD, DME and RVO. It works by targeting 2 key pathways involved in these diseases: VEGF-A and angiopoietin-2 (Ang-2). Faricimab's dual target inhibition disrupts abnormal new blood vessel formation (neovascularization), stabilizes vascular leakage, and targets chronic inflammation, key pathophysiological processes and characteristic of these retinal conditions (Sahni et al., 2019; Sharma et al., 2020). Phase III trials, nAMD - TENAYA/LUCERNE (Heier et al., 2022), DME - YOSEMITE/RHINE (Wykoff et al., 2022; Wong et al., 2023), have shown promising results for faricimab, offering improved efficacy and extended dosing intervals compared to aflibercept.

The European Medicines Agency (EMA) approved faricimab for the treatment of nAMD and DME in September 2022, based on pivotal clinical trial data. However, these randomized clinical trials (RCTs) are usually conducted under very controlled, protocol specific settings, in well-defined patient populations, which may differ in disease severity, patient demographics, treatment patterns and adherence to treatment in the real-world setting.

Real-world evidence studies, such as FaReal, are essential for complementing the findings of clinical trials, providing insights into treatment outcomes in diverse patient populations, assessing long-term effectiveness and safety, understanding treatment patterns, evaluating healthcare resource utilization, and facilitating comparative effectiveness research. These studies play a crucial role in informing clinical practice, optimizing treatment strategies, and improving patient care in the management of retinal diseases.

